3.2 Interim Analysis

As described in [Section 10.7](#), an interim analysis will be conducted when two-thirds of the ITT population have completed 72 hours of efficacy assessments (approximately 41 participants per arm). Based upon the interim analysis results, recommendation from the DMC, and agreement from the Sponsor, the study will either continue without modification or will transition to enrollment in an open-label phase. All participants enrolled in the open-label phase will receive open-label ganaxolone IV solution added to SE standard of care. The screening, duration of the treatment, and follow-up periods, as well as the study schedule, would remain the same for participants enrolled under either the double-blind or open-label phases as described above and in [Figure 1](#). Approximately 60 to 100 study participants are planned to receive ganaxolone IV in the double-blind and open-label phases combined.

3.3 Duration and Study Completion Definition

The maximum duration of study participation is expected to be approximately 4 weeks.

The study completion date is defined as the date the final participant, across all sites, completes their final study assessment/procedure; this includes the follow-up visit/contact, whichever is later. The study completion date is used to ascertain timing for posting and reporting of study results.

3.4 Sites and Regions

This multicenter study is to be conducted in the United States, Canada, and Australia, with approximately 100 sites planned to participate.

4 STUDY POPULATION

Each participant/participant's parent/guardian/legally authorized representative (LAR) must participate in the informed consent process and provide written informed consent/assent, unless allowed by law, e.g., deferred consent, before any procedures specified in the protocol are performed. Consent/assent will be administered per institution IRB/EC policy and may vary across sites, i.e., some sites may be able to consent/assent over the phone or other communication methods. Informed consent/assent for participants who are known to be at risk for SE may be obtained prior to a SE event. The period the pre-consent/assent is valid will be determined by institution IRB/EC. However, reconsenting will be needed should the consent/assent be updated at any point during the study.

4.1 Inclusion Criteria

The participant will not be considered eligible for the study without meeting all the criteria below.

1. Participant, participant's parent, guardian, or LAR must provide signed informed consent/assent, and once capable (per institution guidelines), there must be documentation of consent/assent by the participant demonstrating they are willing and aware of the investigational nature of the study and related procedures. Where allowed by law, where the patient lacks the capacity to make informed decisions regarding his/her medical treatment options, the treating clinician may follow their deferred consenting practices. The clinician will make the final decision based on the best interests of the patient.
2. Male or females 12 years of age and older at the time of the first dose of IP.
3. SE meeting the following criteria:
 - a. A diagnosis of SE with or without prominent motor features based on clinical and EEG findings according to the investigator's judgement, based on the following:
 - i. For SE with prominent motor features: Clinical and EEG seizure activity indicative of convulsive, myoclonic or focal motor SE
 - ii. For SE without prominent motor features (nonconvulsive SE): Appropriate clinical features and an EEG indicative of NCSE (see modified Salzburg criteria¹⁹ in Appendix 3).
 - iii. For any type of SE:
 - Approximately 6 minutes of cumulative seizure activity over a 30-minute period within the hour before IP initiation, AND
 - Seizure activity during the 30 minutes immediately prior to IP initiation.
 - b. The treating clinician(s) anticipate that IV anesthesia is likely to be the next treatment for SE that persists following initiation of IP.
4. Participants must have received any two or more of the following agents for treatment of the current episode of SE administered at an adequate dose and for a sufficient duration, in the judgment of the investigator, to demonstrate efficacy (guidelines for adequate doses are provided in Appendix 2):
 - Benzodiazepines,
 - IV Fosphenytoin/phenytoin,
 - IV Valproic acid,
 - IV Levetiracetam,
 - IV Lacosamide,
 - IV Brivaracetam, or
 - IV Phenobarbital
5. BMI <40 or, if BMI is not able to be calculated at screening, participant is assessed by investigator as not morbidly obese.

4.2 Exclusion Criteria

Participants are excluded from the study if any of the following exclusion criteria are met.

1. Life expectancy of less than 24 hours.
2. Anoxic brain injury or an uncorrected rapidly reversable metabolic condition as the primary cause of SE (e.g., hypoglycemia <50 mg/dL or hyperglycemia >400 mg/dL).
3. Participants who have received high-dose IV anesthetics (e.g., midazolam, propofol, thiopental, or pentobarbital) during the current episode of SE for more than 18 hours, or who continue to have clinical or electrographic evidence of persistent seizures while receiving high-dose IV anesthetics.
4. Clinical condition or advance directive that would NOT permit use of IV anesthesia.
5. Participants known or suspected to be pregnant.
6. Participants with known allergy or sensitivity to progesterone or allopregnanolone medications/supplements.
7. Receiving a concomitant IV product containing Captisol® (marketed products listed in Appendix 4).
8. Known or suspected hepatic insufficiency or hepatic failure leading to impaired synthetic liver function.
9. Known or suspected stage 3B (moderate to severe; eGFR 44-30 mL/min/1.73m²), stage 4 (severe; eGFR 29-15 mL/min/1.73m²), or stage 5 (kidney failure; eGFR <15 mL/min/1.73m² or dialysis) kidney disease.
10. Use of an investigational product for which less than 30 days or 5 half-lives have elapsed from the final product administration. Participation in a non-interventional clinical study does not exclude eligibility.
11. Known or suspected history or evidence of a medical condition that, in the investigator's judgment, would expose participant to an undue risk of a significant adverse event or would interfere with assessments of safety or efficacy during the study.

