10. Pregnancy test for females of childbearing potential, should be collected predose (screening). Samples can be urine or serum. If unable to collect predose, collect as soon as possible following IP initiation. Enrollment is not contingent upon results. However, if a participant has a positive test result, it will be at the investigator's discretion to weigh the risks versus benefits for enrollment or continued participation. If the institution requires the pregnancy test results to be obtained prior to IP initiation, the institution's guidelines will be followed.
11. Electroencephalogram is required for confirmation of CSE and NCSE diagnosis. Ideally, continuous EEG monitoring should start at least 60 minutes before IP initiation and continue through the end of the first 24 hours of the follow-up period.

Sites will be offered the use of a rapid EEG device to assist with screening of participants with NCSE. It is preferred that a conventional EEG is used for the purposes of confirming inclusion criterion #3 and EEG monitoring during IP administration. In situations when a conventional EEG is not immediately available, the rapid EEG may be used to confirm inclusion criterion #3. Since the rapid EEG has a limited battery life, it should be switched to a conventional EEG within several hours but not earlier than 90 minutes after IP initiation to allow uninterrupted collection of EEG for the 30-minute SE cessation co-primary endpoint. It will be at the investigator's discretion if the use of the rapid EEG will benefit their site. The device should be used according to institution standard practices.

12. Blood sampling (venous or arterial) for pharmacokinetic (PK) analysis of ganaxolone and Captisol® will be collected at the following times:

Required collections:

- a. After the start of the IP infusion: 60 minutes (+/- 5 min), then 2, 6 (+/- 5 min), 10, 24 and 36 hours (+/- 2 hour) following IP initiation,
- b. At the time of IP discontinuation (+/- 1 hour), either at the end of the taper or if the IP administration is stopped without a taper (e.g., when the participant progresses to IV anesthesia for seizure/SE treatment), and
- c. 24 hours (+/- 1 hour) following IP discontinuation.

Variable PK collection times based on participant response:

Between IP initiation and at the end of the first 24 hours of the follow-up period, where possible, collect a PK sample:

- d. At the time of an SAE (related or not related)

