4.4 Reproductive Potential

4.4.1 Female Contraception

Sexually active females of childbearing potential should be using an acceptable form of contraception and must be advised to use acceptable contraceptives throughout the study period and for 30 days after the last dose of IP. If hormonal contraceptives are used, they should be administered according to the package insert.

Females of childbearing potential who are not currently sexually active must agree to use acceptable contraception, as defined below, if they become sexually active during the period of the study and 30 days after the last dose of IP.

Female participants should be:

- Postmenopausal (12 consecutive months of spontaneous amenorrhea and \geq age 51 years), or
- Surgically sterile (having undergone one of the following surgical acts: hysterectomy, bilateral tubal ligation, bilateral oophorectomy, or bilateral salpingectomy) and at least 6 weeks post-sterilization, or
- Should have a urine or serum sample collected for pregnancy testing prior to IP initiation. If not possible, collect as soon as possible following IP initiation. Enrollment is not contingent upon results. However, if a participant has a positive test result, it will be at the investigators' discretion to weigh the risks versus benefit for continued participation. If the institution requires the pregnancy test results be obtained prior to IP initiation, the institution guidelines will be followed.

Acceptable methods of contraception are:

- Intrauterine device plus condoms
- Double barrier methods (e.g., condoms and diaphragm with spermicidal gel or foam)
- Hormonal contraceptives (oral, patch, injectable, or vaginal ring), stabilized for at least 30 days prior to the study participation, plus condoms. Note: If participant becomes sexually active during the study, they should use one of the other acceptable methods noted above in addition to the hormonal contraceptive until it has been stabilized for 30 days.

Contraceptive measures such as Plan BTM, sold for emergency use after unprotected sex, are not acceptable methods for routine use.

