As described in [Table 1](#) and [Section 4.4](#), a urine or serum pregnancy test should be collected for all females of childbearing potential prior to IP initiation, and if pregnancy is suspected. If unable to collect predose, collect as soon as possible following IP initiation. Enrollment is not contingent upon results. However, if a participant has a positive test result, it will be at the investigator's discretion to weigh the risks versus benefits for continued participation. If the investigator decides to discontinue the IP, please refer to [Section 4.5](#). If the institution requires the pregnancy test results be obtained prior to IP initiation, the institution guidelines will be followed.

Blood Gas

All blood gas samples arterial or venous, if collected, will be at the investigator's discretion to manage care. If collected from the time of SE diagnosis through the end of the first 24 hours of the follow-up period, the eCRF should be completed. If samples are not collected, a sample will not be required.

If a decision is made to intubate the participant between IP initiation through the end of the first 24 hours of the follow-up period, a blood sample should be collected. The sample should be collected immediately prior to or as close as possible to the time of intubation.

The clinical laboratory tests performed as part of the protocol are listed in Table 6.

Table 6. Clinical Laboratory Tests

Hematology	Coagulation	Biochemistry	Urinalysis
Hemoglobin (Hb)	Fibrinogen	Sodium	pH
Hematocrit (Hct)	Activated partial thromboplastin time (aPTT)	Potassium	Protein
Red blood cell count (RBC)	Prothrombin time (PT)	Calcium	Blood
White blood cell count; total and differential (WBC)	International normalized ratio (INR)	Glucose	Ketones
Mean corpuscular hemoglobin (MCH)		Total protein	Glucose
Mean corpuscular hemoglobin concentration (MCHC)		Albumin	Bilirubin
Mean corpuscular volume (MCV)		Creatinine	Specific gravity
Platelet count		Blood urea nitrogen (BUN)	If any abnormal value is observed on the urine dipstick test, the sample should be further analyzed with urine microscopy:
WBC Differential		Total Bilirubin	WBC
% Basophils		Alkaline phosphatase (ALP)	RBC
% Eosinophils		Aspartate transaminase (AST)	Cellular casts
% Lymphocytes		Alanine transaminase (ALT)	Granular casts
% Monocytes		Total cholesterol ¹	Hyaline casts
% Neutrophils		Estimated Glomerular Filtration Rate (eGFR), if available	

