11.2.2 Protocol Adherence and Investigator Agreement

The investigator and any sub investigators must adhere to the protocol as detailed in this document. The investigator is responsible for enrolling only those participants who have met protocol eligibility criteria. Investigators are required to sign an investigator agreement to confirm acceptance and willingness to comply with the study protocol.

If the investigator suspends or terminates the study at their site, the investigator will promptly inform the Sponsor and the IRB/EC and provide them with a detailed written explanation. The investigator will also return or destroy all IP, containers, and other study materials in accordance with the Sponsor instructions. Upon study completion, the investigator will provide the Sponsor, IRB/EC, and regulatory agency with final reports and summaries as required by (inter)national regulations.

Communication with local IRBs/ECs, to ensure accurate and timely information is provided at all phases during the study, may be done by the Sponsor, applicable CRO, investigator, or, for multicenter studies, the coordinating principal investigator according to national provisions and will be documented in the investigator agreement.

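### A positive pregnancy test known before dosing is a mandatory exclusion under criterion 5, but synopsis item 10 and Table 1 footnote l leave enrollment to the investigator

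*Protocol*

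**What the plan says.** **The exclusion rule.** Protocol 4.2 opens with "Participants are excluded from the study if any of the following exclusion criteria are met". Criterion 5 on that list is "Participants known or suspected to be pregnant", and the synopsis carries the same criterion. No judgment is attached to it, whereas criterion 11 on the same list expressly calls on the investigator's judgment. Protocol 11.2.2 adds: "The investigator is responsible for enrolling only those participants who have met protocol eligibility criteria".

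**The testing rule.** Synopsis item 10 asks for a urine or serum pregnancy test before dosing in females of childbearing potential, or as soon as possible after IP initiation if that cannot be done. It then says "Enrollment is not contingent upon results" and leaves a positive test to the investigator's "discretion to weigh the risks versus benefits for enrollment or continued participation". Table 1 footnote l says the same, and the SAP schedule (section 8.1, footnote l) repeats it.

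**Other places.** Protocol 4.4.1 and 7.2.3.7 also say that enrollment does not depend on the result, but they give discretion over continued participation only: "discretion to weigh the risks versus benefit for continued participation" in 4.4.1 and "discretion to weigh the risks versus benefits for continued participation" in 7.2.3.7. Section 8.1.6 likewise mentions only continued participation.

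**Enrollment.** Protocol 6.2.2.1 defines it as the start of the IP infusion and bars IP until eligibility has been determined.

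**The concern.** A site holding a positive predose test can find two instructions in the same protocol. Under criterion 5 the participant is out. Under synopsis item 10 and footnote l the investigator may weigh risk and benefit and enroll her. An investigator who uses that discretion to enroll follows item 10 but departs from 4.2 and 11.2.2.

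The point matters for two reasons. The criterion protects participants, and the trial admits females from age 12 in an emergency setting, often with surrogate or deferred consent, where staff need one rule they can apply quickly. It also affects reporting. SAP 3.1.2 looks for deviations in the inclusion and exclusion criteria and summarizes them by category, so the same case could be counted as an eligibility deviation or regarded as allowed by the protocol.

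**Working it through.** No figure in the plan bears on this, so the check is a comparison of the texts.

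**Step 1: which results can the discretion cover?** Item 10 names two decisions, enrollment and continued participation. Enrollment is the start of the infusion (6.2.2.1). A decision about enrollment can only rest on information available before that moment. The discretion therefore cannot be read as limited to results that come back late.

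**Step 2: does criterion 5 apply to such a result?** A participant with a positive predose test is at least suspected to be pregnant, so criterion 5 is met and 4.2 excludes her.

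**Step 3: compare the rules case by case.**

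| Situation at IP initiation | Criterion 5 | Item 10 / footnote l | Conflict? |
|---|---|---|---|
| Positive result already known | Excluded | Investigator may enroll or not | Yes: decisions can be opposite |
| Pregnancy suspected on other grounds, no result yet | Excluded | Discretion is tied to a positive test; the text says only that enrollment does not depend on the result | Unclear: suspicion is not addressed |
| No result, pregnancy not suspected | Not met | Enrollment may proceed | No |
| First positive result after initiation | Not met at entry | Discretion over continued participation | No |

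**Step 4: does another clause settle the first row?** Item 10 and footnote l defer to institutions that require the result before IP initiation. That governs when the result must be available, not what follows if it is positive.

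**Step 5: which analyses could be touched?**
- The Safety population is everyone who received IP (SAP 2.2.1).
- The ITT population is everyone randomized in the double-blind phase who received IP and has an efficacy assessment (SAP 2.2.2). Neither definition refers to eligibility.
- The Per Protocol population drops only major deviations tied to the co-primary efficacy assessments (SAP 2.2.3; Protocol 10.3).
- The deviation summary and listing (SAP 3.1.2) do use the eligibility criteria, so the classification matters there.

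**The case against.** The strongest reply is that the texts can mostly be read together. The discretion permits enrollment and does not require it, so an investigator who excludes every participant with a known positive test complies with both rules. In 4.4.1 and 7.2.3.7, the sentence on enrollment follows an instruction to test after initiation if predose collection was not possible, and the discretion there covers continued participation only. The natural meaning is that treatment need not wait for a result, which fits criterion 5. Footnote l is a combined paragraph on drugs of abuse, alcohol and pregnancy, and synopsis item 9 uses the same discretion sentence for drug and alcohol testing, so in the footnote it is less specific to pregnancy. Sections 4.2, 6.2.2.1 and 11.2.2 together suggest that the exclusion list governs. Finally, randomization has stopped, so new wording is unlikely to change an enrollment decision.

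Most of this stands, and it sets the limits of the point. A reader might infer that the two rules always give opposite decisions, or that 4.4.1, 7.2.3.7 and 8.1.6 contradict criterion 5 outright. The documents do not support either inference: the discretion is permissive, and those three sections can be read consistently with the criterion. But the reply does not remove the conflict in synopsis item 10, which concerns pregnancy testing alone and names enrollment explicitly. Nor does the protocol say which text prevails; that would have to be inferred.

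**Conclusion.** The inconsistency is real and lies in current operative text. It is confined to pregnancy known or suspected before IP initiation, with a positive predose test as the clear case. There, mandatory exclusion stands beside discretion to enroll.

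Its size cannot be given. The documents do not say how many participants had a positive predose test, and the number may be zero. Protocol 3.1.1 reports that randomization stopped at 100. SAP 1.3.1 makes open-label enrollment depend on an efficacy finding at the interim, and the documents report only a recommendation to continue without modification. The practical consequence left is therefore the classification of any case already enrolled, plus any further use of this text.

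A reader might also infer that the Per Protocol analysis is at risk. That does not follow. That set excludes only major deviations related to the co-primary efficacy assessments, and nothing in the documents links a pregnancy eligibility deviation to SE cessation at 30 minutes or to progression to IV anesthesia by 36 hours. No effect on the ITT or Safety populations is shown.

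The conclusion assumes that a positive test counts as at least suspected pregnancy, and that enrollment carries the meaning given in 6.2.2.1 wherever it appears.

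**What to change.** Reconcile criterion 5 (Protocol 4.2 and synopsis) with synopsis item 10, Table 1 footnote l and SAP footnote l, so that a positive result known before IP initiation has one stated consequence. Align the sentence on enrollment in 4.4.1 and 7.2.3.7 with that consequence, and make clear whether it means only that dosing need not wait for a result. The sponsor and its clinical advisers must choose the rule; this review does not propose one.

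For the data in hand, compare the time of each positive pregnancy result with the start of infusion, using the pregnancy listing planned in SAP 3.3.3 and source records where needed. Check also for pregnancy recorded as suspected before dosing. Then apply the single rule to every such participant when classifying eligibility deviations under SAP 3.1.2, before database lock, and report the count even if it is zero.

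The cost is a clarification memo or a short wording change and a brief data check. No analysis population or test changes.

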4.3 Restrictions

Participants must abstain from the use of alcohol until the end of the 24-hour IP discontinuation follow-up period.

Females are prohibited from breastfeeding for 45 days after the last dose of IP.

4.4 Reproductive Potential

4.4.1 Female Contraception

Sexually active females of childbearing potential should be using an acceptable form of contraception and must be advised to use acceptable contraceptives throughout the study period and for 30 days after the last dose of IP. If hormonal contraceptives are used, they should be administered according to the package insert.

Females of childbearing potential who are not currently sexually active must agree to use acceptable contraception, as defined below, if they become sexually active during the period of the study and 30 days after the last dose of IP.

Female participants should be:

- Postmenopausal (12 consecutive months of spontaneous amenorrhea and \geq age 51 years), or
- Surgically sterile (having undergone one of the following surgical acts: hysterectomy, bilateral tubal ligation, bilateral oophorectomy, or bilateral salpingectomy) and at least 6 weeks post-sterilization, or
- Should have a urine or serum sample collected for pregnancy testing prior to IP initiation. If not possible, collect as soon as possible following IP initiation. Enrollment is not contingent upon results. However, if a participant has a positive test result, it will be at the investigators' discretion to weigh the risks versus benefit for continued participation. If the institution requires the pregnancy test results be obtained prior to IP initiation, the institution guidelines will be followed.

Acceptable methods of contraception are:

- Intrauterine device plus condoms
- Double barrier methods (e.g., condoms and diaphragm with spermicidal gel or foam)
- Hormonal contraceptives (oral, patch, injectable, or vaginal ring), stabilized for at least 30 days prior to the study participation, plus condoms. Note: If participant becomes sexually active during the study, they should use one of the other acceptable methods noted above in addition to the hormonal contraceptive until it has been stabilized for 30 days.

Contraceptive measures such as Plan BTM, sold for emergency use after unprotected sex, are not acceptable methods for routine use.

